### **3.4 DOSE MODIFICATIONS/DELAY**

Dose modifications are not permitted.

3.4.1 Doses will be delayed for the following:

- Any Grade 2 or greater drug-related adverse event with the following exceptions:
  - Grade 2 skin rash or fatigue
  - Grade 2 infusion reaction in which the full dose of the drug is safely infused, per instructions in section 3.4.4
- Any adverse event, laboratory abnormality, or intercurrent illness which, in the judgment of the investigator, warrants delaying the dose of study medication.
- Algorithms for management of toxicities are provided in Section 12.3.

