### 3.4.2 Resuming treatment

Subjects may resume treatment with avelumab under any of the following circumstances:

- Any grade 2 event that resolves to grade 1 or less within 14 days without systemic steroid treatment
- Grade 3/4 rash that improves to Grade 1/2 with treatment
- Grade 2/3/4 endocrinopathy that responds to treatment/replacement therapy

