### 14.3 APPENDIX C: MANAGEMENT OF IMMUNE-RELATED ADVERSE EVENTS

#### Immune-Related Adverse Events

Since inhibition of PD-L1 stimulates the immune system, immune-related AEs (irAEs) may occur. Treatment of irAEs is mainly dependent upon severity (NCI-CTCAE grade):

Grade 1 to 2: treat symptomatically or with moderate dose steroids, more frequent monitoring

Grade 1 to 2 (persistent): manage similar to high grade AE (Grade 3 to 4)

Grade 3 to 4: treat with high dose corticosteroids

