14.3.5 Cardiac AEs

Cardiac irAEs		
Myocarditis	Management	Follow-up
New onset of cardiac signs or symptoms and / or new laboratory cardiac biomarker elevations (e.g. troponin, CK-MB, BNP) or cardiac imaging abnormalities suggestive of myocarditis.	
Withhold avelumab therapy Hospitalize.
 
In the presence of life threatening cardiac decompensation, consider transfer to a facility experienced in advanced heart failure and arrhythmia management.
 
Cardiology consult to establish etiology and rule-out immune-mediated myocarditis.
 
Guideline based supportive treatment as per cardiology consult.*
 
Consider myocardial biopsy if recommended per cardiology consult.
	
If symptoms improve and immune-mediated etiology is ruled out, re-start avelumab therapy.
 
If symptoms do not improve/worsen, viral myocarditis is excluded, and immune-mediated etiology is suspected or confirmed following cardiology consult, manage as immune-mediated myocarditis.

Immune-mediated myocarditis	
Permanently discontinue avelumab.
 
Guideline based supportive treatment as appropriate as per cardiology consult.*
 
Methylprednisolone 1 to 2 mg/kg/day.
	
Once improving, taper steroids over at least 1 month and add prophylactic antibiotics for opportunistic infections.
 
If no improvement or worsening, consider additional immunosuppressants (e.g. azathioprine, cyclosporine A)

*Local guidelines, or eg. ESC or AHA guidelines            ESC guidelines website: https://www.escardio.org/Guidelines/Clinical-Practice-Guidelines            AHA guidelines website: http://professional.heart.org/professional/GuidelinesStatements/searchresults.jsp?q=&y=&t=1001
		

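### Section 3.4.2 permits re-dosing after suspected Grade 2 myocarditis that settles early, while Appendix C 14.3.5 still withholds the drug because the cause is open

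*Combined protocol and SAP*

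**What the plan says.** Section 3.4.1 of the protocol delays a dose for "Any Grade 2 or greater drug-related adverse event with the following exceptions"; the exceptions are Grade 2 rash or fatigue and certain Grade 2 infusion reactions. Section 3.4.2 sets the terms for restarting: "Subjects may resume treatment with avelumab under any of the following circumstances". The first circumstance is "Any grade 2 event that resolves to grade 1 or less within 14 days without systemic steroid treatment". The other two cover Grade 3/4 rash and Grade 2 to 4 endocrinopathy. Section 3.4.3 makes discontinuation permanent only for drug-related events of Grade 3 or 4, apart from those that 3.4.2 allows back.

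The event-specific rules are in section 14.3, "APPENDIX C: MANAGEMENT OF IMMUNE-RELATED ADVERSE EVENTS". The cardiac table, 14.3.5, opens with this trigger: "New onset of cardiac signs or symptoms and / or new laboratory cardiac biomarker elevations"; suggestive imaging abnormalities also count. No grade is attached. The first instruction is "Withhold avelumab therapy Hospitalize", followed by a cardiology consult to find the cause. The restart condition is "If symptoms improve and immune-mediated etiology is ruled out, re-start avelumab therapy". A second row, for immune-mediated myocarditis, ends avelumab for good and starts methylprednisolone at 1 to 2 mg/kg/day.

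The link between the two parts is one sentence in 3.4.1: "Algorithms for management of toxicities are provided in Section 12.3". Section 12 is the pharmaceutical information and contains only 12.1 and its subsections.

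**The concern.** The body of the protocol releases a patient on grade, time and absence of steroids. The appendix releases on cause. For most toxicities that difference does no harm, but for suspected myocarditis the cause is what decides whether another dose is acceptable. A patient whose symptoms fade quickly can satisfy the body's test while the question that the appendix insists on is unanswered.

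The situation is realistic. Doses fall every 14 days (3.2.1.1), and a work-up that may extend to myocardial biopsy (14.3.5) can still be pending when the next one is due. Shortness of breath is one of the myocarditis symptoms checked before each dose (3.3.1), and severe papillomatosis itself impairs breathing (1.2.4), so an early answer on cause cannot be assumed.

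The stake is patient safety: re-exposure of someone with possible immune-mediated myocarditis. The protocol already treats the event as special. It is an adverse event of special interest (7.1.6), and its symptoms are also checked by telephone weekly between on-site assessments (3.3.4). The resumption rule does not reflect that. Sample size, error rates and the primary endpoint are not affected.

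**Working it through.** No arithmetic applies beyond a count. The check sets the two rules side by side and asks, for each type of case, whether 3.4.2 permits a dose that 14.3.5 withholds.

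**Scope.** Suspected myocarditis that improves within 14 days, with no systemic steroid given up to the resumption decision. Cases are crossed by grade (1, 2, 3 to 4) and by the state of the immune work-up (ruled out, open, confirmed): 3 × 3 = 9 cells.

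| Grade | Immune cause | 3.4.2 | 14.3.5 | Conflict |
|---|---|---|---|---|
| 1 | ruled out, open or confirmed (3 cells) | rule does not reach Grade 1 | as its own branches say | 0 |
| 2 | ruled out | permits | restart allowed | 0 |
| 2 | open | permits | withhold stands | 1 |
| 2 | confirmed | ceases to apply once steroid starts | permanent stop plus steroid | 0 |
| 3 to 4 | ruled out, open or confirmed (3 cells) | no permission (rash and endocrinopathy only) | as its own branches say | 0 |

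Total: 0 + 0 + 1 + 0 + 0 = 1 of 9.

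**The open-cause cell, step by step.**

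1. Section 3.4.2 is met. One circumstance suffices, the event was Grade 2, it fell to Grade 1 or less in time, and no steroid was given.
2. The restart branch of 14.3.5 is not met. It has two joint conditions, and the second, exclusion of an immune cause, fails.
3. The branch of 14.3.5 that leads to management as immune-mediated disease is not met either. It requires symptoms that persist or worsen, and here they improve.
4. With neither branch met, the standing instruction in 14.3.5 is still to withhold. Because the second branch is not entered, the appendix triggers no steroid, so the steroid condition in 3.4.2 does not block resumption.

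**The confirmed Grade 2 cell.** The second row of 14.3.5 stops the drug and starts methylprednisolone at 1 to 2 mg/kg/day. Section 3.4.2 then no longer applies, and 3.6.1 removes a patient who needs more than 10 mg of prednisone equivalents daily. On that reading the texts agree. If one looks instead at the moment before the steroid starts, 3.4.2 does not forbid a dose and 3.4.3 does not reach Grade 2, so the count would be 1 + 1 = 2 of 9. The count of 1 is the cautious one, and the open-cause conflict stands on either reading.

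**Does another rule close the gap?**

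- 3.4.3 covers only Grade 3 or 4 drug-related events.
- 3.6.1 has no myocarditis criterion, and its steroid criterion is not met here.
- 7.1.6 and 7.3 govern reporting. Admission makes the event serious under 7.1.2 and reportable within 24 hours, but reporting is not a hold.
- 3.7.1 pauses the trial for a treatment-related death or three unexpected serious events of Grade 3 or higher, so a Grade 2 case does not count.
- No statement of precedence between section 3.4 and Appendix C was found.

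**The case against.** The strongest reply is that nobody is forced into error. Section 3.4.2 is permissive, whereas 14.3.5 is a directive, so an investigator who follows the appendix breaches nothing. A specific algorithm is naturally read as overriding a general permission. Section 3.4.1 also delays a dose whenever the investigator judges that an event warrants it, 3.6.1 allows removal on the same kind of judgment, and the team discusses each patient every two weeks (6.4.1). All of this stands, and it is why the matter is a correction to make rather than a grave hazard. But judgment allows a delay without requiring one, and the precedence of the specific rule is left to the reader.

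The wrong section number is said to be clerical. That is fair: the pointers to the performance status, voice index and Derkay appendices carry the same offset, and the table of contents lists 14.3 by title. On its own it would be trivial. It matters a little more here because it is the only pointer in 3.4 to the stricter rule.

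The Grade 2 premise is open to challenge. Section 14.3.5 sends every suspected case to hospital, and the infusion-reaction table in 3.4.4 associates hospitalization with Grade 3. If suspected myocarditis were always Grade 3 or higher and drug-related, 3.4.3 would stop treatment and the conflict would vanish. That table does not grade myocarditis, though, and the appendix trigger is ungraded and can be met by biomarkers alone. The point stands as an assumption, not as a refutation.

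Finally, the appendix never says in terms that restart is allowed only when an immune cause is excluded; it simply has no branch for an improved patient with the cause open. True, but withholding is its standing order, and it offers no other way back.

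**Conclusion.** The concern holds. For suspected Grade 2 myocarditis that settles within 14 days without systemic steroids while the cause is undetermined, section 3.4.2 permits a dose that 14.3.5 withholds, and the protocol does not say which text prevails. The conflict is over what is permitted; an investigator can comply with both by taking the stricter course.

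It affects 1 of 9 grade-by-cause combinations. That is a count of logical cases, not a frequency. The documents give no myocarditis rate, so how often the case would arise cannot be estimated, and it is assumed to be low. The conclusion also assumes that some suspected cases would be graded 2, since the CTCAE grading of myocarditis is not reproduced, and that the appendix hold continues until its restart condition is met. Confidence is medium. The correction should be made because the possible harm is serious and the change is small.

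**What to change.** 1. In 3.4.2, add to the Grade 2 bullet: *except suspected or confirmed myocarditis of any grade, which follows Appendix C 14.3.5 (no restart until an immune-mediated cause is ruled out)*. This alone removes the conflict.
2. In 3.4.3, add a bullet: *immune-mediated myocarditis, any grade*. This brings the body into line with the second row of 14.3.5 and settles the confirmed Grade 2 case on either reading.
3. In 3.4.1, change the reference for the toxicity algorithms from Section 12.3 to Section 14.3.

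The cost is one phrase, one bullet and one corrected cross-reference, with no extra visits, tests or patients.

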### 3.4.3 Discontinuing treatment

Treatment should be permanently discontinued for the following:

- Any Grade 3 or 4 drug-related adverse event with the exception of criteria listed in [3.4.2](#)

### 3.4.4 Avelumab infusion reactions

Since avelumab contains only human immunoglobulin protein sequences it is unlikely to be immunogenic and induce an infusion or hypersensitivity reaction. However, if such a reaction were to occur, it might manifest with fever, chills, rigors, headache, rash, pruritus, arthralgias, hypo- or hypertension, bronchospasm, or other symptoms. All Grade 3 or 4 infusion reactions should be reported within 24 hours to the sponsor and reported as an SAE if criteria are met. Infusion reactions should be graded according to NCI CTCAE (version 4.0) guidelines.

NCI-CTCAE Grade	Treatment Modification for Study Drug

Grade 1 – mild Mild transient reaction; infusion interruption not indicated; intervention not indicated.
	
Remain at bedside and monitor subject until recovery from symptoms.
 
Decrease the study drug infusion rate by 50% and monitor closely for any worsening. Complete the remainder of the infusion at the reduced rate (50% of initial infusion rate).
 
The total infusion time for study drug should not exceed 4 hours.

Grade 2 – moderate Therapy or infusion interruption indicated but responds promptly to symptomatic treatment (for example, antihistamines, NSAIDs, narcotics, corticosteroids, bronchodilators, IV fluids); prophylactic medications indicated for ≤ 24 hours.
	
Stop study drug infusion. Once infusion-related reaction has resolved or decreased to Grade 1 in severity, resume infusion at 25% of previous rate for 15 minutes, then increase to 50% of previous rate, and monitor closely for any worsening.
 
The total infusion time for study drug should not exceed 4 hours.

Grade 3 or Grade 4 – severe or life-threatening; urgent intervention indicated. Grade 3: Prolonged (for example, not rapidly responsive to symptomatic medication and/or brief interruption of infusion); recurrence of symptoms following
	
Immediately discontinue infusion of study drug. Begin an IV infusion of normal saline, and treat the subject as follows. Recommend bronchodilators, epinephrine 0.2 to 1 mg of a 1:1,000 solution for subcutaneous administration or 0.1 to 0.25 mg of a 1:10,000 solution injected slowly for IV administration, and/or diphenhydramine 50 mg IV with

initial improvement; hospitalization indicated for other clinical sequelae [e.g., renal impairment, pulmonary infiltrates]). Grade 4: (life-threatening; pressor or ventilator support indicated).	methylprednisolone 100 mg IV (or equivalent), as needed. Subject should be monitored until the investigator is comfortable that the symptoms will not recur. Study drug will be permanently discontinued. In the case of late-occurring hypersensitivity symptoms (e.g., appearance of a localized or generalized pruritus within 1 week after treatment), symptomatic treatment may be given (e.g., oral antihistamine, or corticosteroids). Subjects must be withdrawn immediately from study drug treatment and must not receive any further study drug treatment.
--	---

IV = intravenous; NCI-CTCAE = National Cancer Institute-Common Terminology Criteria for Adverse Event; NSAIDs = nonsteroidal anti-inflammatory drugs.

Once the avelumab infusion rate has been decreased by 50% or interrupted due to an infusion-related reaction, it must remain decreased for all subsequent infusions. If a subject experiences a Grade 3 or 4 infusion-related reaction at any time, the subject must discontinue study drug.

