3.1.2 Protocol Schema

### **3.2 DRUG ADMINISTRATION**

#### **3.2.1 Avelumab**

Avelumab will be administered at a dose of 10 mg/kg IV every other week for up to 12 weeks total (6 cycles). All patients will be pre-treated with an antihistamine and acetaminophen 30-60 minutes prior to each dose (for example, 25-50 mg diphenhydramine and 500-650 mg acetaminophen). Avelumab is to be diluted in 250 mL of 0.45% or 0.9% saline solution (sodium chloride injection) and administered as an IV infusion, using a volumetric pump with a 0.2/0.22 micron in-line filter at the protocol-specified dose. It is not to be administered as an IV push or bolus injection.

Avelumab will be infused at 60 mL/hour for 10 minutes; if no infusion reaction observed then rate will be increased to 120 mL/hour for 10 minutes; if no infusion reaction observed then rate will be increased to 250 mL/hour for the remainder of the infusion. If infusion reactions are observed, the infusion rate may be decreased to the previous rate at which it was tolerated. At the end of the infusion, flush the line with a sufficient quantity of normal saline.

Avelumab will be infused in the NIH Clinical Center Day Hospital or on an inpatient oncology ward. Vital signs (blood pressure, pulse, respiration, temperature) will be assessed before infusion, at each rate change, at completion of infusion, and every 1 hour (+/- 15 minutes) or more frequently as clinically indicated for 2 hours after completion of the infusion or until stable.

Medications readily available for the emergency management of anaphylactoid reactions should include: epinephrine (1:1000, 1 mg/mL) for subcutaneous injection, diphenhydramine hydrochloride for intravenous injection, and resuscitation equipment.

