#### 12.1.5 Preparation

Avelumab drug product must be diluted in 250 mL of 0.45% or 0.9% saline solution (sodium chloride injection) supplied in an infusion bag. Detailed information on infusion bags and medical devices to be used for the preparation of the dilutions and subsequent administration will be provided in the manual of preparation.

Prior to the preparation of the dilution for final infusion, allow each vial to equilibrate to room temperature. Use a disposable syringe equipped with a needle of suitable size to remove a volume of sodium chloride solution to be replaced by avelumab from the infusion bag and discard the removed solution. Use a new disposable syringe equipped with a needle of suitable size to inject a volume of avelumab drug product identical to the discarded volume of sodium chloride solution into the infusion bag. Gently invert the mixture 10 times. Infusion bags must not be shaken, in order to avoid foaming or excessive shearing of the protein solution. The preparation must be carefully inspected as it should result in a homogeneous looking clear solution, free of visible particles.

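### After an infusion reaction in the first rate step, the Section 3.4.4 rate cuts cannot deliver the 250 mL bag within that table's own 4-hour cap; in the second step they narrowly miss it

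*Combined protocol and SAP*

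**What the plan says.** **Volume and rates.** Section 3.2.1: "Avelumab is to be diluted in 250 mL of 0.45% or 0.9% saline solution". Section 12.1.5 has saline withdrawn first, then tells staff to "inject a volume of avelumab drug product identical to the discarded volume of sodium chloride solution into the infusion bag", so the bag stays at 250 mL. The schedule is "Avelumab will be infused at 60 mL/hour for 10 minutes", then, if no reaction is seen, "rate will be increased to 120 mL/hour for 10 minutes", then 250 mL/h to the end.

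**Reaction rules in Section 3.4.4.**
- Grade 1: halve the rate, then "Complete the remainder of the infusion at the reduced rate (50% of initial infusion rate").
- Grade 2: stop. Once the reaction has settled, restart at a quarter of the *previous* rate for 15 minutes, then go to half of it.
- Both rows: "The total infusion time for study drug should not exceed 4 hours".
- Text under the table keeps the reduction in force for every later infusion.

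**Reaction rule in Section 3.2.1.** If a reaction is seen, "the infusion rate may be decreased to the previous rate at which it was tolerated". No grade is named.

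**Dose rules.** Section 3.4 opens with "Dose modifications are not permitted". Section 3.4.1 spares a Grade 2 infusion reaction from dose delay only when the whole dose has been safely given under Section 3.4.4.

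**The concern.** A rate cut and a time cap in the same table cell should be achievable together. Delivering 250 mL in 4 h needs an average of 250/4 = 62.5 mL/h, and half of either of the first two rates (30 or 60 mL/h) is below that. Staff facing an early reaction would have to exceed the cap, depart from the rate rule or leave drug in the bag, and the protocol does not say which. Patients with the same reaction could then be handled differently and receive different exposure.

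Response is first assessed after three doses (Section 3.1.1), so one half-delivered dose would be 0.5/3, about 17%, of planned first-course exposure. Section 12.1.4 lists infusion-related reaction among the most frequent treatment-related events, so the table is likely to be used.

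**Working it through.** **Inputs.** Volume 250 mL (Sections 3.2.1 and 12.1.5). Step 1: 60 mL/h for 10 min = 10 mL. Step 2: 120 mL/h for 10 min = 20 mL. Step 3: the remaining 220 mL at 250 mL/h. Rate cuts and cap from Section 3.4.4. The plan states no total infusion time. Without a reaction it is 10 + 10 + (220/250) × 60 = 72.8 min.

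**Method.** Total time = time elapsed at the reaction + remaining volume ÷ reduced rate, evaluated at the start and end of a step. For Grade 2, add 15 min at a quarter of the rate. The length of the pause is not given and is set to zero, the most favourable case.

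**Grade 1, cut taken from the rate at the time of the reaction**
- Step 1 (30 mL/h): start 250/30 = 8.33 h; end 0.17 + 240/30 = 8.17 h. Given by 4 h: 4 × 30 = 120 mL, or 10 + 3.83 × 30 = 125 mL, which is 48-50%.
- Step 2 (60 mL/h): start 0.17 + 240/60 = 4.17 h; end 0.33 + 220/60 = 4.00 h. Given by 4 h: 240-250 mL, or 96-100%.
- Step 3 (125 mL/h): longest at the start, 0.33 + 220/125 = 2.09 h.

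**Grade 2, previous rate = rate at the time of the reaction, pause = 0**
- Step 1: the slow 15 min delivers 15 × 0.25 = 3.75 mL. Start 0.25 + 246.25/30 = 8.46 h; end 0.17 + 0.25 + 236.25/30 = 8.29 h.
- Step 2: the slow 15 min delivers 30 × 0.25 = 7.5 mL. Start 0.17 + 0.25 + 232.5/60 = 4.29 h; end 0.33 + 0.25 + 212.5/60 = 4.12 h (4.125 unrounded). That is 7.5-17.5 min over, before the pause.
- Step 3: the slow 15 min delivers 62.5 × 0.25 = 15.6 mL. Start 0.33 + 0.25 + 204.4/125 = 2.22 h, leaving about 1.8 h for the pause.

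| Reaction during | Grade 1 | Grade 2, before pause | Within 4 h? |
|---|---|---|---|
| 60 mL/h | 8.17-8.33 h | 8.29-8.46 h | No, about twice the cap |
| 120 mL/h | 4.00-4.17 h | 4.12-4.29 h | Grade 1 only at the very end of the step; Grade 2 no |
| 250 mL/h | at most 2.09 h | at most 2.22 h | Yes, for Grade 2 if the pause is under about 1.8 h |

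**If *initial* in the Grade 1 row means the 60 mL/h starting rate.** The remainder runs at 30 mL/h whenever the reaction occurs. At the start of step 3: 0.33 + 220/30 = 7.67 h. With x mL remaining during step 3, the cap is met when 0.33 + (220 − x)/250 + x/30 ≤ 4, so x ≤ 95 mL. At least 155 mL must already be in, which is reached at 20 + (125/250) × 60 = 50 min. Earlier Grade 1 reactions breach the cap.

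**Section 3.2.1 step-back rule.** From 250 to 120 mL/h: at most 0.33 + 220/120 = 2.17 h. From 120 to 60 mL/h: 4.00-4.17 h. At 60 mL/h there is no earlier rate.

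**Later infusions.** A flat 30 mL/h takes 8.33 h, a flat 60 mL/h 4.17 h and a flat 125 mL/h 2.00 h. Halving every step takes 0.33 + (250 − 5 − 10)/125 = 2.21 h. Section 3.4.4 does not say which is meant.

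**The case against.** Most of the infusion is not affected. The 250 mL/h step carries 220 of 250 mL (88%) and 52.8 of 72.8 min (73%), and reactions there fit the cap when the cut is from the current rate. A reader might infer that no reduced-rate infusion can be completed; the figures do not support that. In the second step the Grade 1 overrun is 0-10 min. The documents give no timing of reactions, so the number of patients affected is unknown.

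The 7.67 h figure is also not a settled consequence of the rules. The Grade 1 row first says to halve the rate and then refers to the reduced rate, so *initial* can naturally mean the rate just before the cut. Reading it as 60 mL/h would turn a third-step reaction into an 88% cut (250 to 30 mL/h). That argument stands as far as it goes: the word is ambiguous, and the Grade 2 row uses *previous* instead.

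A reader might further infer that a truncated infusion breaches the ban on dose modifications. Section 3.4 does not say that stopping short counts as one. Section 3.4.1 in fact foresees an incomplete Grade 2 infusion, because its exemption from delay depends on the full dose being given.

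Lastly, Section 3.2.1 is permissive and Section 3.4.4 is specific by grade, and stepping back from 120 to 60 or from 250 to 120 mL/h is a cut of 50% or 52%. For Grade 1 the two rules therefore nearly agree after the first step. They still differ for Grade 2, where one lowers the rate and the other stops the infusion, and the step-back rule has nothing to return to in the first step.

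None of this removes the first-step conflict, which holds on either reading of *initial*. Halving each later step (2.21 h) would fit, but the Grade 1 row completes the remainder at the reduced rate and the Grade 2 row describes no return to higher rates.

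**Conclusion.** The concern holds for early reactions. In the first 10 minutes the rate cut and the cap are incompatible by a factor of about two, for both grades. In the next 10 minutes they are incompatible by minutes, except for a Grade 1 reaction at the very end of the step. For Grade 2 reactions in either step, the Section 3.4.1 exemption, which requires the full dose under Section 3.4.4, cannot be earned within the cap. Third-step reactions are compatible, unless the Grade 1 cut is taken from 60 mL/h and the reaction comes before about minute 50.

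This rests on a 250 mL bag, the cap counted from the start of the infusion, no return to higher rates after the cut, and a zero pause for Grade 2. Any pause that counts toward the cap widens the Grade 2 overrun. Whether an incomplete infusion is a dose modification is left open by the documents. Nothing here shows an effect on the complete-response endpoint or the two-stage design in Section 9.

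**What to change.** The sponsor should reconcile Sections 3.2.1, 3.4, 3.4.1 and 3.4.4 so that the 250 mL volume, the rate reductions and the 4-hour cap can be met together. The text should:
- use one defined term for the rate from which a cut is taken, in place of *initial* and *previous*;
- say how Section 3.2.1 relates to the graded table, including in the first step and for Grade 2;
- say whether a pause counts toward the cap;
- say how a reduction carries over to later stepped infusions;
- say what applies, and how the dose is recorded and classed under Sections 3.4 and 3.4.1, when the cap is reached with drug remaining.

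Which rate, cap or clinical rule to adopt is for the sponsor and clinical team. The cost is a protocol wording amendment, with no change to sample size or visits.
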